## 1.0 TRIAL SUMMARY

Abbreviated Title	Neoadjuvant Pembro And Rads for Sarcoma
Trial Phase	Pilot Study
Clinical Indication	Localized soft tissue sarcomas
Trial Type	Single-arm, open label
Type of control	Historical
Route of administration	IV
Trial Blinding	None
Treatment Groups	All subjects receive standard of care radiation therapy + pembrolizumab
Number of trial subjects	26
Estimated enrollment period	12 months
Estimated duration of trial	3 years
Duration of Participation	Treatment in 3 months (subjects will be followed up to for 5 years)
Estimated average length of treatment per subject	3 months

## 2.0 COMMONLY USED ABBREVIATIONS:

AE	Adverse Event
APC	Antigen Presenting Cell
APP	Advanced Practice Provider (Nurse practitioners or physician assistants)
BMP	Basic Metabolic Panel
CBC	Complete Blood Count
CMP	Complete Metabolic Panel
CR	Complete Response
CRF	Case Report Forms
CTCAE	Common Terminology Criteria for Adverse Events
CTL	Cytotoxic T Lymphocyte
DLT	Dose Limiting Toxicity
DSMB	Data Safety Monitoring Board
Gy	Gray
EBRT	External Beam Radiation Therapy
ECI	Events of Clinical Interest
ECOG	Eastern Cooperative Oncology Group
IB	Investigator Brochure
IMRT	Intensity Modulated Radiation Therapy
IO	Immuno-oncology
IV	Intravenous
mAb	Monoclonal Antibody
MHC	Major Histocompatibility Complex

OS	Overall Survival
OTC	Over the Counter
PD-1	Programed Death Receptor 1
PD-L1 & 2	Program Death Receptor Ligands 1 & 2
PFS	Progression-free Survival
RECIST	Response Evaluation Criteria in Solid Tumors
RR	Response Rate
SAE	Serious Adverse Event
SD	Stable Disease
SBRT	Stereotactic Body Radiation Therapy
STS	Soft Tissue Sarcoma
TSH	Thyroid Stimulating Hormone
Treg	Regulatory T cell

### 3.0 TRIAL DESIGN

[figure not shown]
#### 3.1 Introduction

Although localized sarcoma is potentially curable, approximately 50% of subjects with large or high-grade tumors will ultimately develop incurable disease. This is a pilot study to examine the addition of the anti-PD-1 targeted, monoclonal-antibody pembrolizumab to standard, neoadjuvant radiation for subjects with high-risk soft tissue sarcomas planning for surgery with curative intent. Pembrolizumab has been combined in the past using hypofractionated radiation, but has never been combined with conventionally fractioned radiation with curative intent in soft tissue sarcoma subjects before. This trial will confirm the safety of this novel combination. A large randomized trial would be required to definitively demonstrate a relapse-free-survival benefit in this population. This study will instead focus on characterizing T-cell responses to this neoadjuvant combination, with a particular focus on the repertoire of tumor infiltrating lymphocytes (TIL). Tumor necrosis and radiographic response by RECIST criteria will be used as surrogates for efficacy, as has been done in other pilot trials combining radiation with novel therapies.

#### 3.2 Treatment Plan

This is an open-label, single-arm, pilot study. Subjects will have localized, intermediate or high grade, large STS tumors.

Figure 1 - Study Schema

Subjects will receive neo-adjuvant radiation per institutional standards, generally 50 Gy given over 5-6 weeks. Subjects will receive their first pembrolizumab dose 1 week prior to

starting radiation. Pembrolizumab will then be administered every 3 weeks, for a maximum of 3 infusions. The standard approved dosing schedule for pembrolizumab will be used in this study, which is a flat 200 mg dose intravenously every 3 weeks. Surgery will be performed as per standard of care, typically 4-6 weeks after the completion of neoadjuvant radiation.

### **3.3 Safety Monitoring on Study and Post-Treatment Follow-Up**

Enrollment will begin with a single cohort of three subject slots. No additional enrollment will be permitted until the first three subjects have completed a full treatment schedule (defined as C1D1 of pembrolizumab through the End of Treatment visit). This temporary pause and review of data is to ensure thorough safety monitoring of the first three subjects enrolled. The data will be reviewed to ensure that pembrolizumab in combination with radiation therapy does not increase the toxicity profile of either treatment in a manner that is unexpected or compromises subject safety.

During this initial 3-subject enrollment, if one or more of the three subjects experiences a serious unexpected adverse event at least possibly related to pembrolizumab or radiation treatment, the temporary enrollment hold will be extended as the Sponsor-Investigator evaluates the potential risk and safety. During this enrollment hold, the Sponsor-Investigator will review all currently collected safety data and make an evaluation as to whether to permit further accrual.

If none of the first three subjects experience a serious unexpected adverse event related to pembrolizumab or radiation treatment, enrollment may continue without restriction. If at any point in time there is greater than 30% of subjects who have unexpected, probably related SAEs grade III or higher that do not resolve to grade 2 within 2 weeks, the trial will pause enrollment for safety review by the Sponsor-Investigator.

All subjects will have an End of Treatment visit 30 days ( $\pm$  14 days) after the completion of pembrolizumab therapy, which may coincide with the pre-operative visit. Subjects will have a Wound Care Follow-Up visit 30 days ( $\pm$  14 days) after their first standard of care post-operative visit to determine how the wound healing is proceeding. If there are wound healing complications or any other ongoing toxicities related to treatment at that time, the subject will continue to be monitored until the toxicity/complication resolves, improves to maximal anticipated improvement, or the study closes.

Subjects will be followed for as many as 5 years after completing treatment for survival determination. This may be done via publicly available records, medical record review, or by phone.

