#### **7.3.2 Radiation Related Toxicities**

The expected toxicities related to radiation therapy may vary in relation to the site of irradiation. The most commonly observed toxicities include fatigue (Grade 3), and skin toxicities (Grade 3) such as rash, color changes, burning, blistering, or desquamation. Skin toxicities should be managed by radiation-oncology staff utilizing standard of care protocols.

The radiation oncologist may list expected toxicities for a given radiation treatment prior to administration of radiation treatment in the subject's medical record. Strict prospective

quality assurance of all radiation plans will be performed prior to initiation of radiotherapy, per institutional standards, to minimize risk of serious toxicity.

Toxicities of radiation should be treated according to standard institutional practices, including the prescription of steroids, if appropriate. Subjects will continue treatment if steroids are used to treat radiation-associated toxicity.

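### The hold, the release and the 30% pause in section 3.3 count only events that are *unexpected*, a word the plan does not define, so they are narrower than the safety aim stated in the same section

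*Combined protocol and SAP*

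**What the plan says.** Protocol section 3.3 stops enrollment after three subjects and has their data reviewed to ensure that the combination "does not increase the toxicity profile of either treatment in a manner that is unexpected or compromises subject safety". Three operative sentences follow:

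- **Extending the hold:** one or more of the three subjects has a "serious unexpected adverse event at least possibly related to pembrolizumab or radiation treatment".
- **Releasing it:** if none of the three has a "serious unexpected adverse event related to pembrolizumab or radiation treatment, enrollment may continue without restriction".
- **Later pause:** "greater than 30% of subjects who have unexpected, probably related SAEs grade III or higher", with the further condition that the event has not come down to grade 2 within two weeks.

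The documents do not define *unexpected* or name a reference for it. Section 7.3.2 is the one place that describes expected toxicities: "The expected toxicities related to radiation therapy may vary in relation to the site of irradiation". It gives fatigue and skin toxicity, both at Grade 3, as the commonest, and adds: "The radiation oncologist may list expected toxicities for a given radiation treatment prior to administration".

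Four other controls bear on the point:

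- Section 9.4.2.1 sends SAEs in the reporting window to the Sponsor-Investigator within 24 hours.
- Section 7.6 makes the incidence or severity of adverse drug reactions a ground for early termination.
- Section 12.0 has committees look at adverse events and stopping rules at least once a year, or more often if needed. Their approval, where applicable, is a condition for continuing.
- Section 9.4.1 records all adverse events from consent to the Wound Care Follow-Up visit.

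**The concern.** The review aim has two limbs joined by *or*: toxicity that is unexpected, or toxicity that endangers subjects. The hold extension, the release sentence and the 30% pause carry only the first limb.

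This matters because of what the trial tests. Radiation is standard care and pembrolizumab is added to it. One direct way for the combination to do harm is to make a known radiation toxicity more frequent, more severe or slower to resolve. That is the kind of event most likely to be called expected. Section 3.1 nevertheless says: "This trial will confirm the safety of this novel combination".

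At stake is whether enrollment pauses when it should. For subjects 4 to 26 the 30% rule is the only trigger with a number in it. Enrollment is estimated at 12 months (section 1.0) and scheduled committee review need only be annual, so a scheduled review could come when accrual is almost or fully complete.

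**Working it through.** **1. Aim and rules side by side (section 3.3).**

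| Sentence | Unexpected toxicity | Toxicity of an expected type that endangers subjects |
|---|---|---|
| Aim of the first-cohort review | covered | covered |
| Hold extension (1 or more of 3) | counted | not mentioned |
| Release | must be absent | not mentioned |
| Pause (more than 30%) | counted | not mentioned |

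**2. What is counted under each reading of *unexpected*.** Take a subject with a skin event that is Grade 3, meets an SAE criterion, is related to treatment and is still above grade 2 after two weeks.

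- *Read by event type:* section 7.3.2 lists the type, so the event is not counted. If 3 of 3 subjects have it, the hold count is 0 of 3 and the release condition is met. If 26 of 26 have it, the pause count is 0/26 = 0%, which does not exceed 30%. No assumed rate is needed.
- *Read by severity or frequency:* the event might count, but the plan gives no radiation-alone rate or severity standard to judge it against.

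**3. The plan's own safety figure.** Section 10.1 gives about a 94% chance of observing a toxicity with 10% prevalence in 26 subjects. Check: 1 − 0.90^26 = 0.935, which agrees after rounding. It is the chance of seeing at least one case and does not say how often either trigger would act. The plan gives no such figure for the triggers.

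**4. What counting these events would cost.** For illustration, keep the 30% limit and drop only the word *unexpected*. Let p be the probability that a subject has a qualifying event (assumed, since the documents give none). Enrollment pauses at the first n where the count exceeds 0.30n, so the boundary is floor(0.3n) + 1: 2 at n = 4, 4 at n = 10, 7 at n = 20 and 8 at n = 26.

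Among paths not yet paused, f_n(k) = (1 − p)·f_(n−1)(k) + p·f_(n−1)(k − 1). At each check the probability at or above the boundary is removed and added to the pause probability. The single look is P(X ≥ 8 | 26, p). Subjects are taken as independent, with two-week status known at each check.

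| p | Checked from n = 4 | Checked from n = 10 | Single look at n = 26 |
|---|---|---|---|
| 5% | 3.5% | 0.3% | <0.1% |
| 10% | 13.4% | 3.9% | 0.3% |
| 15% | 28.5% | 14.5% (0.1445) | 3.2% |
| 30% | 79.7% | 72.0% | 54.0% |
| 40% | 95.8% | 93.9% | 87.8% |
| 50% | 99.6% | 99.4% | 98.6% |

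If p is the background rate under radiation alone, the first three rows are the price in unneeded pauses. The last three show how such a rule would respond if the combination made these events common. Much of the price comes from small early denominators. At p = 15% the first check alone gives 1 − 0.85^4 − 4(0.15)(0.85^3) = 1 − 0.5220 − 0.3685 = 0.110 of the 0.285.

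**The case against.** The strongest reply is that the gap depends on one reading of an undefined word. A reader might infer that listed toxicities can never trigger a hold or pause, so that the chance is zero at every rate. The documents do not support that without the condition. The aim sentence speaks of toxicity increased in an unexpected manner, which can cover severity, duration or frequency. Section 7.3.2 does not say that hospitalization, or failure to resolve in two weeks, is expected. This stands, and the point is therefore conditional. The alternative reading cannot be applied as written, however, because nothing says what excess is measured against.

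A reader might also infer that three serious skin events in the first cohort would go unexamined. They would not. The pause and data review take place whatever occurs, the review aim includes subject safety, and the release sentence only permits enrollment to continue. Expectedness decides whether the hold is automatically extended.

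Sections 7.6 and 12.0 are not limited to unexpected events, and committee approval is a real control. What remains is that these controls work by judgment and contain no count.

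Two further limits are fair. Grade 3 is not the same as serious, so the test case must meet every condition in step 2. Nor does the plan say whether the immune-related events in Table 3 are expected, so it cannot be concluded that they drop out too.

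Finally, leaving out expected events is a defensible choice in a single-arm pilot, where toxicity from radiation alone cannot be separated from toxicity of the combination. The 28.5% figure shows the cost of counting them. That is a reason to choose the limit and the first check with care, but it does not reconcile the rules with the stated aim.

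**Conclusion.** The point holds in conditional form. It is certain from the text that section 3.3 states an aim with two limbs, that its three operative sentences carry one of them, and that *unexpected* has no definition. If the word is read by event type, serious, related, unresolved toxicity of a listed type contributes 0 of 3 and 0 of 26 to the triggers. If it is read by severity or frequency, the rule lacks a reference and cannot be applied consistently. Either way the section needs rewording.

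The consequence is limited. Such events would be recorded, reported and reviewed, and could lead to action at the discretion of the Sponsor-Investigator or the committees. What is missing is a numeric trigger for them among subjects 4 to 26. This is a cheap improvement that should be made; it does not show that the trial lacks safety oversight. The pause probabilities rest on assumed rates, independent subjects and prompt outcome information. They illustrate the trade-off and do not measure the plan's performance.

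**What to change.** Reconcile the hold extension, the release sentence and the 30% pause in section 3.3 with the aim stated there, so that serious related events that endanger subjects can extend the hold or count toward the pause whether or not their type is listed as expected. State whether *unexpected* is judged by type, severity or frequency. If it is frequency, name the radiation-alone reference. The sponsor chooses any limit and when checking starts; a short table such as the one in step 4, for the rule chosen, would show what it does.

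The cost is a wording change. Adverse events are already recorded through the Wound Care Follow-Up visit, so no new data or visits are needed. A frequency reference would take some work, because the documents contain no radiation-alone rate. The running cost is some pauses for toxicity that radiation alone would cause: with the 30% limit, 3.5% to 28.5% when checked from n = 4, or 0.3% to 14.5% from n = 10, over assumed background rates of 5% to 15%. Each would be an enrollment pause for review by the Sponsor-Investigator, not termination of the trial.

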### **12.0 DATA AND SAFETY MONITORING PLAN**

Institutional support of trial monitoring will be in accordance with the FHCC/University of Washington Cancer Consortium Institutional Data and Safety Monitoring Plan. Under the provisions of this plan, FHCC Clinical Research Support (CRS) coordinates data and compliance monitoring conducted by consultants, contract research organizations, or FHCC employees unaffiliated with the conduct of the study. Independent monitoring visits occur at specified intervals determined by the assessed risk level of the study and the findings of previous visits per the institutional DSMP.

In addition, protocols are reviewed at least annually and as needed by the Consortium Data and Safety Monitoring Committee (DSMC), FHCC Scientific Review Committee (SRC) and the FHCC/University of Washington Cancer Consortium Institutional Review Board (IRB). The review committees evaluate accrual, adverse events, stopping rules, and adherence to the applicable data and safety monitoring plan for studies actively enrolling or treating subjects. The IRB reviews the study progress and safety information to assess continued acceptability of the risk-benefit ratio for human subjects. Approval of committees as applicable is necessary to continue the study.

The trial will comply with the standard guidelines set forth by these regulatory committees and other institutional, state and federal guidelines.

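### After a clean three-subject run-in, the only numeric pause rule is a running proportion above 30%, so one related death can never pause enrollment and several need not

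*Combined protocol and SAP*

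**What the plan says.** Section 3.3 of the protocol sets two enrollment rules.

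- **First three subjects.** The hold is extended "if one or more of the three subjects experiences a serious unexpected adverse event at least possibly related to pembrolizumab or radiation treatment". One event is enough, and any serious grade counts.
- **Afterwards.** If the three are clean, "enrollment may continue without restriction", subject to one numeric rule, applied at any point in time. Its condition reads "greater than 30% of subjects who have unexpected, probably related SAEs grade III or higher that do not resolve to grade 2 within 2 weeks". When that condition is met, "the trial will pause enrollment for safety review by the Sponsor-Investigator".

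No sentence in 3.3 treats a fatal event separately.

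Other sections bear on safety without giving a count:

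- Section 9.4.2.1 requires deaths from any cause during treatment and the defined follow-up window to reach the Sponsor-Investigator within 24 hours and the drug supplier within 2 working days.
- Section 7.6 lists the incidence or severity of adverse drug reactions among the grounds for early termination.
- Section 12.0 says that "protocols are reviewed at least annually and as needed by the Consortium Data and Safety Monitoring Committee (DSMC"), together with the Scientific Review Committee and the IRB, and makes continuation depend on the approval of committees as applicable.
- Section 13.3 lets the Sponsor-Investigator or the FDA terminate the study.

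The Trial Summary (1.0) gives the "Estimated enrollment period" as 12 months and the sample size as 26.

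**The concern.** At subject 4 the rule loosens in three ways at once: from one event to more than 30% of subjects, from possibly to probably related, and from any serious unexpected event to one of Grade 3 or higher that persists. A death and a Grade 3 event that takes 15 days to improve carry equal weight.

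Section 3.1 describes the disease as potentially curable, says this combination with conventional fractionation has not been given before in this setting, and makes confirming its safety an aim of the trial. Three clean subjects are thin reassurance: an event with a true rate of 10% is absent from all three with probability 0.9³ = 73%. In a trial of this size the realistic question is what happens after the first or second related death. On that, 3.3 is silent.

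**Working it through.** **Plan's own figure.** The documents give no operating characteristic for the 30% rule. The nearest figure, in Section 10.1, is a 94% chance of observing a toxicity of 10% prevalence among 26 subjects: 1 − 0.9²⁶ = 93.5%, which agrees to the nearest percent.

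**Inputs.** N = 26. The threshold is strictly above 30%, checked at any point in time (3.3). No event occurs in the first three subjects. Every death is taken to be unexpected and probably related. A death cannot resolve, so it meets the persistence condition.

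**Step 1, boundary.** The smallest count k with k/n > 0.30 is floor(0.3n) + 1.

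| Subjects n | Events needed |
|---|---|
| 4–6 | 2 |
| 7–9 | 3 |
| 10–13 | 4 |
| 14–16 | 5 |
| 17–19 | 6 |
| 20–23 | 7 |
| 24–26 | 8 |

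One death gives at most 1/4 = 25%, so it never meets the rule. At the end, 7/26 = 26.9% is below the threshold and 8/26 = 30.8% is above it.

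**Step 2, orderings.** Place D deaths at random among subjects 4 to 26 (23 positions) and check the proportion after each subject. For D = 2 the rule is met only if both deaths fall in subjects 4–6: C(3,2)/C(23,2) = 3/253 = 1.2%. For D = 3, 71 of C(23,3) = 1,771 orderings meet it: 61 with at least two deaths in subjects 4–6, and 10 more with all three in subjects 4–9. Exact enumeration gives the rest.

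| Deaths | Orderings that never trigger | Share |
|---|---|---|
| 1 | 23 of 23 | 100% |
| 2 | 250 of 253 | 99% |
| 3 | 1,700 of 1,771 | 96% |
| 4 | 7,995 of 8,855 | 90% |
| 5 | 27,007 of 33,649 | 80% |
| 7 | 92,623 of 245,157 | 38% |

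**Step 3, illustrative rates.** The documents give no fatal-event rate, so the rates below are assumptions, applied independently to the 23 subjects after the run-in. The running rule is evaluated by exact recursion. A single-death trigger pauses with probability 1 − (1 − p)²³.

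| Assumed rate p | 30% rule pauses | 2+ deaths, no pause | Single-death trigger pauses |
|---|---|---|---|
| 5% | 0.9% | 31% | 69% |
| 10% | 4.4% | 64% | 91% |
| 20% | 24% | 72% | 99% |

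**The case against.** A reader might infer that seven related deaths among 26 subjects would not pause enrollment. The documents do not support that. The rule runs at any point in time, so in 62% of orderings seven deaths cross it before the end. At an assumed 10% rate, exactly seven deaths without a pause has probability 0.17% (3.3% at 20%). Once all 26 are enrolled, a pause would affect only replacements under 7.2.3 and 7.5.

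A reader might also infer that nothing else stands between a death and continued accrual. That is too strong as well. Deaths are reported within 24 hours. Section 7.6 makes severity alone a ground for early termination. Section 12.0 provides as-needed review and independent monitoring at risk-based intervals, and Section 13.3 allows termination at any time. Nor do the documents show that committee review would come too late. A review held only at one year could fall after a 12-month accrual, but Section 12.0 also allows earlier review, and the institutional plan that sets actual timing is not in the documents.

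The assumed death rates are open to challenge. Sections 6.2.2 and 6.2.3.2.2 describe radiation with anti-PD-1 therapy as given without significantly increased toxicity. The results in Step 2 need no assumed rate.

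What survives is narrower. Every other safeguard depends on someone's judgment, and none obliges a pause or a review after a given number of related deaths.

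**Conclusion.** The point holds as a gap in the design, not as an error or a contradiction. After a clean run-in, one related death can never meet the numeric rule, and two to five fail to meet it in 99% to 80% of orderings.

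These results assume that each outcome is known before the next subject enrolls and that the denominator is subjects enrolled so far. The protocol does not define the denominator or say how replaced subjects count. If subjects not yet observed are included, the threshold is crossed later. Treating every death as unexpected and probably related favors the rule: a death from an expected immune-related toxicity would not enter the count. Table 6 also records relatedness only as yes or no, and only for the Merck product, so the rule's probable category has no matching data field.

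This is a worthwhile, inexpensive improvement. It does not imply that the sponsor would ignore a death.

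**What to change.** Add to Section 3.3, alongside the 30% rule, wording such as: *Any death assessed as having a reasonable possibility of relationship to pembrolizumab, radiation or the combination, occurring at any time while enrollment is open, pauses new enrollment until the Sponsor-Investigator's review has been sent to the Consortium DSMC. Such deaths continue to count toward the 30% rule.*

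Three details matter:

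- The causality wording follows the yes/no scale in Table 6 and must be extended to radiation, which Table 6 does not cover.
- The window runs while enrollment is open. It should not end at the Wound Care Follow-Up visit, which Table 5 (footnote 3) allows to be omitted.
- Deaths stay in the 30% count, so the existing rule is not weakened.

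The change governs enrollment only and alters no dose or individual treatment. It costs a short addition to 3.3, a causality entry for radiation, and a possible short accrual pause for a death later judged unrelated. The DSMC already exists.
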